7 METHODS

Current methods of assessing arm volume include volume measurement using repeated tape measurement at predefined intervals along the limb, with the volume being calculated assuming a circular or elliptical truncated cone geometry. This method is tedious and time-consuming to perform. There is no standardisation of the number of circumferential measurements that are required to provide a reasonably accurate measurement of volume and it is thus not considered sufficiently validated to use in the study. Perometry volume determined from the 3D silhouette cast by the limb when passed through a ray of optoelectronic sensors¹⁴ is rapid, accurate and precise, but requires expensive equipment which is not very portable. The total volume of the arm may change for various reasons. The most common is weight gain but work or exercise induced muscle hypertrophy are cases in point where a simple total volume measurement is not immediately related to the parameter of interest i.e lymphatic volume. Additionally, there is dispute about the definition of lymphoedema. Many people have used the definition of greater than 10% arm volume increase compared to the contralateral arm, but others have claimed that a 200ml volume difference between the arms can be used to define unilateral lymphoedema following breast cancer^{11,11}. For the purposes of this study, we are using a greater than 10% arm volume increase measured by perometer on at least two occasions to identify women with lymphoedema secondary to axillary node clearance¹¹⁵¹ Czerniec et al found that perometer compared to bioimpedance spectrometry had a high concordance with bioimpedance $r=0.92$.

Perometer Measurement

The perometer is a standard arm volume measurement device that uses infra-red optoelectronic technology to detect and quantify limb changes. Perometer software then calculates the entire limb

volume and the % difference between the limbs and since a hard copy of each patient's data is retained on the database, it can be used to compare limb volume changes over time. Pre-surgical limb volume measurement accounts for pre-existing normal inter-limb variation which may range from 3-10% depending on arm dominance and activity level¹²⁹¹, hence the need for pre-surgical measurements. The upper limb volume and circumference are calculated by the perometer software (rather than the operator) and a comparison made between the previous reading from the same patient.

A standard operating procedure for the use of a perometer has been developed across all centres for this study and the PLACE trial. At least 2 readings at each visit by the same perometer operator (lymphoedema, research nurse or CTA depending on centre) will be required in the study, to minimise any variability in the measurements. Additionally, before the patient is randomised or considered to have failed intervention, a lymphoedema nurse will be required to repeat the duplicate measurements to confirm the findings.

With regard to the variability of perometer measurements using a standard operating procedure, which involves duplicate bilateral arm measurement of each individual patient produces an inter-observer (day to day) variability of measurements with a 1.2% standard deviation. Given entry to, and exit from, the PLACE trial requires a further confirmatory duplicate measurement by the lymphoedema nursing sister, the likelihood of "migration" across "category" purely due to inter-observer variability will be under 2%. Review of the ALMANAC trial data revealed the mean percentage increase in the volume of operated arms was 4.0% and 5.14% at 3 and 6 months respectively. Thus, the majority of patients who will be eligible will require a near doubling of arms volume before developing lymphoedema (>10% AVI).

Multifrequency Bioimpedance Monitoring

Multi-frequency bioimpedance electrical analysis (BEA) is a non-invasive technique to measure total water content, which involves passing an extremely small electrical current through the body and measuring the impedance (or resistance) to the flow of this current. In recent years the BEA technique has been refined to measure the impedance over a range of frequencies from 4 to 1000kHz. By mathematically modelling the measured data, the impedance at zero frequency (i.e. the impedance of the extracellular fluid alone) can be determined³¹¹. The use of BEA as a measurement tool for the presence of lymphoedema has been previously well-described^{311,315}. Briefly, two measurement electrodes will be placed at either end of a 40 cm long segment of the limb with current drive electrodes placed approximately 10 cm distally. Identical electrode positions will be used on both arms. BEA measurement on each arm will be performed using a U400 multiple frequency BEA (ImpediMed) and will be performed to a standardised method (see SOP in Appendix B). Two results will be recorded:

The ratio of these values comparing the treated and untreated sides of these women with unilateral breast cancer (unaffected arm:affected arm) will be calculated. A patient will be classified as having lymphoedema when the impedance ratio is more than 3 standard deviations above normative data, with the normative data taking into account the significant effect of limb dominance.

- 1) Absolute BEA score (with a greater than 3sd level compared to the contralateral arm and reference leg equalling lymphoedema status);
- 2) Change in BEA score from baseline. Changes from preoperative baseline of >10% increase in BEA would represent a value score identifying lymphoedema using BEA.

All treatment decisions in the study will be based on Perometer measurements as this currently represents the standard of care internationally.

We will assess multi-frequency bioimpedance monitoring compared to perometer arm measurements in women after axillary node clearance (ANC) in 9 centres. We will use

bioimpedance monitoring during the study to determine its value in predicting response to compression garment therapy. Within the study we will assess reproducibility of both methods across centres and robustly establish both intra and interobserver error rates for both methods in the study population.

Please note, this assessment will only be carried out on the initial 1100 recruits, as part of the 5 year study. Subsequent recruits, as part of the 9 month study, will not undergo this as enough data will be gathered from the original cohort.

9 PATIENT SATISFACTION AND LYMPHOEDEMA QUESTIONNAIRE

Study specific patient satisfaction questionnaires will be developed (with input from patient representatives) and reviewed to assess level of utility for each mode of delivery. Also, the preference in patients prior to, and following treatment, will be compared to identify the proportion of patients likely to choose early intervention rather than the conventional approach. Compliance will be assessed by means of patient diaries.

10 DEFINITION OF CELLULITIS

Cellulitis of the arm after axillary node clearance is a recognised complication and will be recorded in the study. Hospital admission with cellulitis for intravenous antibiotics should be recorded in the Case Record Form (CRF). Entry criteria have therefore been based on a confirmed diagnosis of cellulitis by a general physician, dermatologist or dermatology nurse, along with a checklist of presenting features that will be used to describe the study population.

To confirm diagnosis of the recent (index) episode of cellulitis lymphangitis,, evidence that the following 4 signs and symptoms were present must be obtained from the patient's notes or through discussion with the patient:

- Presence or history of local warmth and tenderness or acute pain.
- Unilateral erythema, or asymmetrical erythema with the more severe side having a temporal relationship to symptoms.
- New or increased swelling of the arm.
- Constitutional disturbance (e.g malaise, rigors, fever).

11 ECONOMIC EVALUATION

Early intervention for arm swelling could result in resource savings to the NHS. If we establish that early detection and intervention is successful, cost effectiveness analysis will be carried out to compare any utility benefits to cost differences between the two strategies. Two analyses will be presented: NHS direct costs only, and NHS plus patient/carer direct costs (including lost income but excluding estimated productivity losses). To facilitate this, comprehensive comparison of the costs of the two groups will be undertaken.

For each patient group the following resource data will be collected using hospital records for resource use and patient diary cards for care in the community:-

- 1) Number of outpatient visits (planned and unplanned).
- 2) Resources used in therapy (compression garments).
- 3) Patient/carer trips associated with hospital care (mode of transport and costs).
- 4) Time off work/loss of income associated with chronic lymphoedema care.

Resource data will be validated using the unit costs of the UHSM finance data using appropriate and explicit assumptions regarding staff time and equipment use. Extensive sensitivity analysis will be carried out where assumptions are made. This data should enable a comprehensive comparison of total costs to the NHS in the two groups to be made. Any savings to the NHS will be identified.

In addition to a cost effectiveness analysis, we will estimate the budget and service impact of early intervention (for arm swelling) to the NHS based on the experience of the study and will include the possibility of extending this treatment service to non-specialist centres.

Health Economics Modelling

The additional factor introduced into the modelling described is the comparison of a new diagnostic technology (BEA) with conventional measurement to predict / determine the development of lymphoedema. It is necessary to model the costs and health consequences of the four potential outcomes of a diagnostic test (true or false positive, true or false negative), and to then compare overall costs and benefits of using BEA with conventional measurement in the context of either early preventive intervention or of conventional management of emergent lymphoedema. In practice this will require multiple applications of the long-term model developed for the PLACE Trial with appropriate parameter values and assumptions, combined with the performance characteristics of the diagnostic tests, as a basis for determining whether BEA is a cost-effective technology with or without early preventive intervention.

This is a good example of the economic evaluation of a diagnostic technology, which is a developing field of study in which the economics team already have an interest and are developing experience in the context of the new NICE diagnostics programme.

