1.6 The Multi-frequency Bioimpedance in the Early Detection of Lymphoedema Trial

We will assess multi-frequency bioimpedance monitoring compared to perometer arm measurements in women after axillary node clearance (ANC) in 9 centres for the first 1100 patients enrolled in the 5 year study. We will use bioimpedance monitoring during the study to determine its value in predicting response to compression garment therapy. Within the study we will assess reproducibility of both methods across centres and robustly establish both intra and interobserver error rates for both methods in the study population. Subsequent recruits, as part of the 9 month study, will not undergo this as enough data will be gathered from the original cohort.

All women undergoing ANC in the UHSM Breast Unit have been invited to have preoperative 1,3,6,12 and 18 monthly bilateral arm measurements with a perometer (Pero-Systems 350S) and circumferential arm tape measurements. Of the last 270 women approached undergoing ANC within the last 11 months, 183 (67%) agreed to participate. We will use 9 centres who will monitor women undergoing ANC from pre-surgery baseline with perometer measurements and BEA to compare the sensitivity and specificity of both techniques for predicting chronic lymphoedema development. Identifying the most sensitive and specific method for detecting chronic lymphoedema would enhance selection of patients for intervention with arm sleeves should the intervention prove cost effective. Please note, this assessment will only be carried out in the initial 1100 recruits, as part of the 5 year study.

We have negotiated agreement with the manufacturers for provision and training in the use of L-DEX U400 bioimpedance spectroscopy devices for all centres taking part in the 5 year study with the appropriate software and electrodes to carry out a health technology assessment.

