3.4 Treatment Measurements

For the first 1100 recruits (recruited before January 2015), arm volume will be measured at baseline, 1, 3, 6, 9 and 12 months then 6 monthly thereafter to 2 years, followed by annual measurements to 5 years using perometer arm scanning (and circumferential tape measurement of arm girth with anatomic landmarks (e.g. lateral epicondyle) as reference points). The contralateral arm will act as a control. *For the additional 300 patients (recruited from February 2015, on version 3.1 or higher of the patient information leaflet), these measurements will take place at baseline, 1, 3, 6, and 9 months only.*

Patients developing a 4-8.9% increase in arm volume within 9 months of arm surgery will be offered randomisation. Within the same visit, patients will undergo multi-frequency bioimpedance measurements, comparing the affected arm with the contralateral arm and the leg. Bioimpedance measurements will not lead to change of treatment but will be recorded and performed according to the trial Standard Operating Procedures (please note, Bioimpedance will only be measured in

the 1100 patients who are part of the 5 year study. Subsequent patients, who will only be followed up for 9 months, will not undergo this assessment).

Perometer measurements demonstrating an increase in arm volume >10% (on two occasions) will be utilised to commence treatment for lymphoedema.

For the first 1100 participants, FACT B+4 questionnaires will be administered at all visits apart from the 1 month visit to permit calculation of Trial Outcome Index (FACT B TOD following the ATAC Trial methodology. ^[PG 60] A lymphoedema symptom questionnaire will be administered at the same time points. EQ5D questionnaires will be administered at all time points apart from months 3, 36, 48 and 60.

Please note, quality of life questionnaires will only be administered at baseline for the final 300 participants.

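### Section 11 collects lost income only for chronic lymphoedema care, so the NHS-plus-patient/carer analysis leaves out lost income from early sleeve care and tends to favour early intervention

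*Protocol*

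**What the plan says.** Protocol Section 11 (Economic Evaluation) sets out a cost-effectiveness analysis, to be done if early detection and intervention prove successful. It will be presented twice: with NHS direct costs only, and with patient and carer direct costs added. The second version includes lost income and excludes estimated productivity losses.

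Four resource items are to be collected for each patient group, from hospital records and patient diary cards:

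1. Clinic attendances, whether scheduled or not.
2. What the treatment itself uses, namely compression garments.
3. Travel to hospital by the patient or a carer, with its mode and cost.
4. "Time off work/loss of income associated with chronic lymphoedema care"

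Only item 4 is tied to chronic disease.

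Section 3.4 places the early intervention at a lower level of swelling: "Patients developing a 4-8.9% increase in arm volume within 9 months of arm surgery will be offered randomisation". Sections 1.4 and 7 define lymphoedema as a perometer increase of more than 10% on at least two occasions. Section 5 (Group B) expects about 135 women with 4-8.9% swelling to receive a sleeve in the PLACE trial, and a similar number to enter that trial without one.

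**The concern.** The comparison sets treatment before lymphoedema against treatment once lymphoedema has developed. An item limited to chronic lymphoedema care records the patient's lost income from the second kind of treatment and not from the first. The missing cost is therefore not spread evenly over the two strategies. It sits with the strategy whose value is in question.

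What is at stake is the patient/carer part of the second analysis. If time off for sleeve fitting and early sleeve care is never asked about, the lost-income saving from avoided lymphoedema is counted without the lost income spent in avoiding it. A later analysis plan cannot repair this. Time off work is reported by the patient as it happens, and of the two data sources named, the diary card is the one likely to hold it.

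**Working it through.** The protocol gives no cost or quantity for time off work, so there is no stated figure to reproduce. The check sets the passages side by side and then works out the direction of the omission.

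**Step 1. Does item 4 cover early sleeve care?**

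| Element | Where | Content |
|---|---|---|
| Swelling at which randomisation is offered | Section 3.4; Section 5, Group B | 4-8.9% |
| Definition of lymphoedema | Sections 1.4 and 7 | more than 10%, on at least two occasions |
| Lost-income item | Section 11, item 4 | chronic lymphoedema care only |
| Items 1 to 3 | Section 11 | no limit to chronic disease |

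Section 11 does not define chronic. Even if it is read generously as any lymphoedema under the protocol's definition, the upper limit of 8.9% lies below 10%, so early sleeve care falls outside item 4. The protocol also keeps the two apart in its own language. Section 1.4 speaks of intervening before swelling becomes chronic, and Section 11 (Health Economics Modelling) contrasts early preventive intervention with conventional management of emergent lymphoedema.

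**Step 2. Which way does the omission point?** Write mean lost income per woman as the sum of three parts: S (sleeve care before lymphoedema), M (arm monitoring) and L (lymphoedema care). Use E for early intervention and C for conventional management. Under conventional management no sleeve is applied before lymphoedema, so S_C = 0.

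- True difference, early minus conventional: (S_E + M_E + L_E) − (M_C + L_C)
- Difference collected under item 4: L_E − L_C
- Collected minus true: −(S_E + M_E − M_C)

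S_E cannot be negative. If women managed early are monitored at least as often as the others, M_E − M_C is not negative either. The collected difference is then at or below the true one, so early intervention looks cheaper than it is, or at best equally costly.

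**Step 3. Which part matters?** Inside this study all women in the five-year cohort share one measurement schedule, so M_E and M_C should largely cancel there. Monitoring matters when the strategies are compared with ordinary care, because Section 1.4 says that arm measurement before axillary clearance is not routine. The part that does not cancel in either setting is S_E.

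**Step 4. How large is it?** For every £1 of mean lost income per woman from early sleeve care, the patient/carer cost difference per woman is £1 too favourable to early intervention. With about 135 women in the sleeve group, the uncounted total is 135 × S_E. The protocol gives no value for S_E and nothing from which to derive one. The £220 per patient per year in Section 1.1 is a cost of managing chronic arm lymphoedema, not lost income, and cannot stand in for it.

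**Step 5. What is not affected?** Items 1 to 3 are collected for each group without a disease limit, so garments, visits and trips for early sleeve care are counted. Lost income does not enter the NHS-only analysis.

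**The case against.** The strongest reply has three parts.

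- **Most early-intervention costs are collected.** Garments, outpatient visits and trips are all listed, and one of the two planned analyses does not use lost income. This stands, and it confines the point to one component of one analysis.
- **The details may lie elsewhere.** The protocol's section on the multivariate model says that the economic data come from the PLACE trial, and the diary wording may be set there. That is possible. But Section 11 of this protocol itself states what will be collected, and its wording is restrictive. If the diary is broader, the two need to be aligned.
- **The lost income may be small.** A sleeve fitting may take little time. The documents neither support nor rule this out, which is a reason to collect the data.

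A reader might infer more than the text supports:

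- **That sleeve costs drop out.** They do not: item 2 covers compression garments in each group.
- **That the cost of the bioimpedance (BEA) test drops out.** The list has no line for the measurement, but Section 11 provides for explicit assumptions on staff time and equipment, with sensitivity analysis. Its modelling part compares overall costs with a view to "determining whether BEA is a cost-effective technology with or without early preventive intervention". Test cost is under-specified, not excluded.
- **That the comparison is tilted towards BEA.** Perometer cost is not listed either, and Section 1.4 calls that equipment expensive. No direction follows. Section 1.6 says of supply, "We have negotiated agreement with the manufacturers for provision and training in the use of L-DEX U400 bioimpedance spectroscopy devices for all centres", but gives no terms, so it cannot be concluded that the accounts understate the price.
- **That pricing from one trust biases the result.** Section 11 states "Resource data will be validated using the unit costs of the UHSM finance data". The same prices apply to both strategies, so this bears on generalisability and has no shown direction.

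**Conclusion.** The point holds in narrow form. As worded, item 4 collects lost income from established lymphoedema care and not from sleeve care given before lymphoedema, nor from monitoring. In the NHS-plus-patient/carer analysis this tends to favour early intervention. The amount cannot be calculated from the documents.

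The conclusion rests on three assumptions: that item 4 is applied as written, that early sleeve care causes some lost time or income, and that women managed early are monitored no less than the others. If the first fails because the diary card asks more widely, what remains is an error of wording in Section 11. The NHS-only analysis and the counts of garments, visits and trips stand as planned.

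**What to change.** Reword item 4 of Section 11 along these lines: *time off work or lost income associated with arm monitoring, sleeve care or lymphoedema care*. State that it is collected in the same way in both groups, and put the matching phrase on the patient diary card. If the PLACE documents already define time off work more widely, bring Section 11 into line with them.

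The cost is one phrase in the protocol and one on the diary card. The downside is a slightly less favourable patient/carer cost for early intervention. Periods already recorded under the narrow wording cannot be filled in from the cards and should be reported as such.

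As optional clarification, Section 11 could also list the cost per measurement for both BEA and the perometer. The correction does not depend on it.

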12 INFORMED CONSENT, ETHICAL AND REGULATORY CONSIDERATIONS

12.2 Ethical Approval

This trial will adhere to the principles outlined in the International Conference on Harmonisation Good Clinical Practice (ICH GCP) guidelines. It will be conducted in compliance with the protocol, GCP, the Data Protection Act and other regulatory requirements, as appropriate.

Multicentre Research Ethics Committee (MREC) approval has been obtained for this trial, and Site Specific Assessments (SSAs) will be performed at participating centres. The trials centre will maintain contact with NRES and will submit any protocol amendments. The trials centre will forward any resulting documentation to local centres.

